8.1 Protocol Amendments

Any amendment to this protocol must be agreed to by the Principal Investigator and reviewed by Celgene. Amendments should only be submitted to IRB/EC after consideration of Celgene review. Written verification of IRB/EC approval will be obtained before any amendment is implemented.

8.2 Protocol Deviations

When an emergency occurs that requires a deviation from the protocol for a subject, a deviation will be made only for that subject. A decision will be made as soon as possible to determine whether or not the subject (for whom the deviation from protocol was effected) is to continue in the study. The subject's medical records will completely describe the deviation from the protocol and state the reasons for such deviation. In addition, the Investigator will notify the IRB/EC in writing of such deviation from protocol.

Non-emergency minor deviations from the protocol will be permitted with approval of the Principal Investigator.

9 Data Management

9.1 Analyses and Reporting

Oncore will be used for data entry and analysis. Data will be analyzed and reported after the last patient has been on trial for at least three 28 day cycles. All subsequent data collected will be analyzed and reported in a follow-up clinical report.

9.2 Data Safety Monitoring Plan

Twice a month the data safety and toxicity committee of the joint Comprehensive Cancer Center of the Cleveland Clinic Foundation and Case Western Reserve University Cancer Centers reviews all hematologic and oncologic trials run at either institution to ensure the safety of patients, validity of data, and appropriate termination of trials should undue risks be discovered or if the trial can not be successfully completed.

9.3 Study Auditing

9.3.1 Investigator Responsibilities

Investigator responsibilities are set out in the ICH guideline for Good Clinical Practice (GCP) and in the US Code of Federal Regulations.

Investigators must enter study data onto CRFs or other data collection system. The Investigator will permit study-related audits by Celgene or its representatives, IRB/EC review, and regulatory inspection(s) (e.g., FDA, EMEA, TPP), providing direct access to the facilities where the study took place, to source documents, to CRFs, and to all other study documents.

The Investigator, or a designated member of the Investigator's staff, must be available at some time during audits to review data and resolve any queries and to allow direct access to the subject's records (e.g., medical records, office charts, hospital charts, and study related charts) for source data verification. The data collection must be completed prior to each visit and be made available to the Celgene representative so that the accuracy and completeness may be checked.

10 Biostatistical Analysis

10.1 Overview

The phase I 3x3 design with 10 additional patients at the highest tolerated low dose (HTLD / HTLD-CKD) of azacitidine as a small phase II extension will lead to a patient accrual of up to 44 patients if the highest dose level is reached. Safety, efficacy, and mechanism of action will be analyzed. [name] will perform the statistical analysis of all clinical endpoints outlined below. The correlative science will be analyzed utilizing the Illumina Bead Studio TM software version 3 with support from [name].

10.2 Datasets to be Analyzed

10.2.1 Dose Limiting Toxicity

Dose limiting toxicity is defined as any one of the following drug-related toxicities occurring during the first 28-day cycle (if a DLT is attributed to progressive disease, it will not be counted as a DLT):

- Any CTCAE v.4.0 grade ≥ 3 non hematologic toxicity (including febrile neutropenia)
 - For nausea, vomiting, or diarrhea, subjects must have a Grade 3 or 4 event that persists at this level despite the use of optimal symptomatic treatment, in order for these events to be considered a DLT
 - Grade 4 transaminitis (serum transaminase $> 20 \times$ upper limit of normal [ULN]) is a DLT, while Grade 3 transaminitis (serum transaminase $> 5 \times$ and $\leq 20 \times$ ULN) must be present for ≥ 7 days to be considered a DLT
 - Grade 3 or 4 venous thromboembolic events are not considered to be DLTs as long as anticoagulant therapy can be administered (see Section 6.5.3 and 6.6.2)

- Grade 3 or 4 hypokalemia, hypophosphatemia, hypomagnesemia or hyponatremia that responds to electrolyte supplementation within 7 days would not qualify as a DLT.
- CTCAE v.4.0 grade ≥ 4 neutropenia or thrombocytopenia that does not resolve to grade ≤ 3 within seven days of holding azacitidine and lenalidomide

Dose limiting toxicity will be assessed weekly during the first cycle. The highest tolerated low dose will be determined as described in Section 5.1.

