5.1 Overall Design

This phase I/II trial will use a classical 3x3 design to determine the highest tolerated low dose (HTLD) for patients with GFR $\geq 60 \text{ ml/min}$ (Cockroft-Gault) and a modified 3x3 design to identify the highest tolerated low dose for patients with GFR 30-59 ml/min (HTLD-CKD) with additional enrollment of 10 patients at the highest tolerated low doses (HTLD / HTLD-CKD) of azacitidine.

Dose levels are outlined under 5.6.2.3.

Dose limiting toxicity (DLT) is defined as one of the following drug-related toxicities occurring during the first 28-day cycle (if a DLT is attributed to progressive disease, it will not be counted as a DLT):

- Any CTCAE v.4.0 grade ≥ 3 non hematologic toxicity (including febrile neutropenia)
 - For nausea, vomiting, or diarrhea, subjects must have a Grade 3 or 4 event that persists at this level despite the use of optimal symptomatic treatment, in order for these events to be considered a DLT

- Grade 4 transaminitis (serum transaminase $> 20 \times$ upper limit of normal [ULN]) is a DLT, while Grade 3 transaminitis (serum transaminase $> 5 \times$ and $\leq 20 \times$ ULN) must be present for ≥ 7 days to be considered a DLT
- Grade 3 or 4 venous thromboembolic events are not considered to be DLTs as long as anticoagulant therapy can be administered (see Section 6.5.3 and 6.6.2)
- Grade 3 or 4 hypokalemia, hypophosphatemia, hypomagnesemia or hyponatremia that responds to electrolyte supplementation within 7 days would not qualify as a DLT.
- CTCAE v.4.0 grade ≥ 4 neutropenia or thrombocytopenia that does not resolve to grade ≤ 3 within seven days of holding azacitidine and lenalidomide. While platelet transfusions are allowed at the discretion of the treating physician to maintain 100% dose level, any grade ≥ 4 thrombocytopenia that is followed by platelet transfusion prior to resolution to grade ≤ 3 will be counted as DLT.

Dose escalation for patients with GFR $\geq 60\text{ml/min}$:

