At least 3 patients will be treated in each dose level tested beginning with dose level 1. At any dose level, if none of the first 3 evaluable patients experience DLT in the first 28 day cycle, the next three patients will be treated at the next dose level. At any dose level, if DLT occurs in one out of three patients during the first 28 day cycle, up to 3 additional patients will be treated at the same dose level. If no DLT occurs in the additional 3 patients, subsequent 3 patients will be treated at the next dose level. Once DLT occurs in 2 patients treated at a given dose level no further patients will be accrued at this dose level but patients already on treatment will continue according to study protocol. If DLT occurs in 2 patients treated at a given dose level, the next lower dose level will be evaluated as the possible HTLD, and if only 3 patients had been enrolled at this dose level, an additional 3 patients will be enrolled to properly assess this dose level as the possible HTLD. The dose level at which DLT occurs in ≤ 1 out of 6 patients will be defined as the highest tolerated low dose (HTLD) and ten more patients will be accrued at this dose level. Six evaluable patients must be assessed for DLT at any dose level that is being considered as the HTLD. Patients experiencing a DLT during their first 28-day cycle may remain on study with appropriate dose reduction (5.7.3).

Dose escalation for patients with GFR 30-59ml/min:

Only two dose levels of azacitidine will be tested in combination with fixed dose lenalidomide. Starting with dose level “CKD 1” (DL CKD1), 3 patients will initially be enrolled and if no more than 1 experience DLT, 3 additional patients will be enrolled at the same dose level. If no more than 1 out of 6 patients treated at DL CKD1 develop DLT, subsequent patients will be enrolled at DL CKD2. Once 2 of 3 or 2 of up to 6 patients treated at a given dose level develop DLT, no further patients will be enrolled at that dose level. If this occurs at DL CKD1, subsequent patients will be enrolled at DL CKD-1. If it occurs at DL CKD2, DL CKD1 will be defined as HTLD-CKD. If 2 of 3 or 2 of up to 6 patients treated at DL CKD-1 develop DLT, the tested azacitidine / lenalidomide / dexamethasone regimen will be considered intolerable for patients with

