Thrombocytopenia \geqGrade 3 (platelet count $< 50,000/\text{mm}^3$)	
 During the first 4 cycles platelet transfusions may be used at the discretion of the treating physician to achieve platelet counts $\geq 50,000/\text{mm}^3$ on post-transfusion CBCs and thereby maintain the current dose level of lenalidomide and azacitidine. If platelet transfusions are administered, the CBC should be monitored at least twice a week. For thrombocytopenia \geq grade 3 ($< 50,000/\text{mm}^3$) after platelet transfusion or if platelet transfusions are not used hold (interrupt) lenalidomide and, while on combination, also azacitidine dose. If thrombocytopenia \geq grade 4 ($< 25,000/\text{mm}^3$) on a pre-platelet transfusion CBC or if platelet transfusions are not used hold prophylactic anticoagulation Follow CBC weekly, if given platelet transfusions twice a week. If thrombocytopenia resolves to \leq grade 4 ($\geq 25,000/\text{mm}^3$) and last platelet transfusion ≥ 7 days ago resume prophylactic anticoagulation. During combination therapy with lenalidomide and azacitidine: 
 If thrombocytopenia resolves to \leq grade 2 (with or without the use of platelet transfusions) prior to Day 21 of the current cycle, restart azacitidine at the next lower dose level and lenalidomide at the same dose level if the patient's myeloma has not previously been refractory to lenalidomide, otherwise maintain azacitidine dose level and reduce lenalidomide by one dose level (if the patient is only on one of these drugs reduce its dose by one level). Otherwise, omit treatment for remainder of cycle and reduce dose levels in the same way at the start of the next cycle. Omitted doses are not made up. During maintenance therapy with lenalidomide: 
 If thrombocytopenia has resolved to \leq grade 2 prior to Day 21 of the current cycle, restart lenalidomide at the next lower dose level, and continue through the scheduled end of the cycle. Otherwise, omit lenalidomide for the remainder of the cycle and reduce lenalidomide by 1 dose level at the start of the next cycle. Omitted doses are not made up.

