6.2.1 Dose Limiting Toxicity Reporting

Dose limiting toxicity (DLT) is defined as one of the following drug-related toxicities occurring during the first 28-day cycle (if a DLT is attributed to progressive disease, it will not be counted as a DLT):

- Any CTCAE v.4.0 grade ≥ 3 non hematologic toxicity (including febrile neutropenia)
 - For nausea, vomiting, or diarrhea, subjects must have a Grade 3 or 4 event that persists at this level despite the use of optimal symptomatic treatment, in order for these events to be considered a DLT
 - Grade 4 transaminitis (serum transaminase $> 20 \times$ upper limit of normal [ULN]) is a DLT, while Grade 3 transaminitis (serum transaminase $> 5 \times$ and $\leq 20 \times$ ULN) must be present for ≥ 7 days to be considered a DLT
 - Grade 3 or 4 venous thromboembolic events are not considered to be DLTs as long as anticoagulant therapy can be administered (see Section 6.5.3 and 6.6.2)
 - Grade 3 or 4 hypokalemia, hypophosphatemia, hypomagnesemia or hyponatremia that responds to electrolyte supplementation within 7 days would not qualify as a DLT.
- CTCAE v.4.0 grade ≥ 4 neutropenia or thrombocytopenia that does not resolve to grade ≤ 3 within seven days of holding azacitidine and lenalidomide.

The PI has to be informed about the occurrence of DLT within one working day after the sub investigator or nurse becomes aware of it. The PI may not allow further accrual at a given dose level once two patients have developed DLT. The PI has to inform Celgene within 5 working days of any DLT with a brief description of the nature of the DLT.

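### The DLT lists in Sections 6.2.1 and 10.2.1 leave out the Section 5.1 rule on transfused grade 4 thrombocytopenia, so such a cycle 1 case could be reported late or missed

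*Combined protocol and SAP*

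**What the plan says.** Section 5.1 (Overall Design) ends its haematologic DLT bullet with a rule on transfusion. It notes that "platelet transfusions are allowed at the discretion of the treating physician to maintain 100% dose level", and then counts as a DLT any grade 4 or worse "thrombocytopenia that is followed by platelet transfusion prior to resolution to grade" 3 or lower. No seven-day wait applies to such a patient.

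Section 6.2.1 (Dose Limiting Toxicity Reporting) prints its own DLT definition. It matches Section 5.1 except that it stops before the transfusion rule, and it does not refer to Section 5.1 for the definition. The same section sets the notices: "The PI has to be informed about the occurrence of DLT within one working day" of staff becoming aware, and "The PI has to inform Celgene within 5 working days of any DLT". It also repeats the accrual stop at two DLTs.

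Section 10.2.1 (Dose Limiting Toxicity, in the statistics chapter) prints the same shorter list. Its haematologic item covers only "neutropenia or thrombocytopenia that does not resolve to grade" 3 or lower within seven days of holding azacitidine and lenalidomide. Its last sentence sends the determination of the highest tolerated low dose (HTLD) to Section 5.1, but it does so after giving its own definition of DLT.

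Table 5 in Section 5.7.5 allows platelet transfusion in the first four cycles to bring the count to at least 50,000/mm³ and "thereby maintain the current dose level of lenalidomide and azacitidine".

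**The concern.** A primary safety endpoint should have one definition. Here there are two, and they disagree for a patient whom the protocol itself foresees: one who reaches grade 4 platelets in cycle 1, is transfused, and has no other DLT.

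The Section 5.1 rule is needed because transfusion can mask the toxicity. Without it, a patient kept on full dose by transfusion never has drug held, so the seven-day test has no starting point. A patient whose drug is held, and whose transfused count improves within seven days, does not meet the shorter test either.

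The first thing at stake is notification. Section 6.2.1 is where site staff look for how to report a DLT, and its list does not cover this patient. The second is the DLT tabulation, because Section 10.2.1 gives the analyst the shorter list. A dose decision is at stake only if the patient is also left out of the count. One patient can then be enough, because at most 1 DLT in 6 is tolerated and 2 are not.

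**Working it through.** **Comparing the three lists.** The stem, the non-haematologic items and their exceptions, and the seven-day haematologic item are the same in Sections 5.1, 6.2.1 and 10.2.1. The only difference in content is the transfusion sentence, which is in Section 5.1 alone.

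| Cycle 1 patient, drug-related grade 4 platelets, no other DLT | 5.1 | 6.2.1 and 10.2.1 |
|---|---|---|
| Drug held, not transfused, still grade 4 after 7 days | DLT | DLT |
| Transfused while grade 4, drug never held | DLT | not a DLT |
| Transfused while grade 4, drug held, grade 3 or lower within 7 days | DLT | not a DLT |

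**Which list governs what.** The synopsis and Section 4.2.1 define DLT by reference to Section 5.1. Section 5.6.1 ties escalation to Section 5.1, and Section 10.2.1 ties the HTLD to it. Section 5.1 also has its own stop: "Once DLT occurs in 2 patients treated at a given dose level no further patients will be accrued at this dose level". If Section 5.1 is applied, the effect of the omission on a dose decision is zero. The DLT notices in Section 6.2.1 have no such reference.

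**The plan's own figure.** The stated maximum of 44 patients reproduces from the synopsis: 18 − 2 = 16 treated at dose levels 1 to 4, plus 6 at level 5, plus 12 with GFR 30–59 ml/min, plus 10 in the extension: 16 + 6 + 12 + 10 = 44. The correction does not change it.

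**Illustration of size.** The documents give no rate for this event, so the rates below are assumptions. Let q be the probability that transfused grade 4 thrombocytopenia is a patient's only DLT, and b the probability of any other DLT.

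*Chance of at least one such patient among six:* 1 − (1 − q)^6.
- q = 0.02: 1 − 0.98^6 = 0.114
- q = 0.05: 1 − 0.95^6 = 0.265
- q = 0.10: 1 − 0.90^6 = 0.469

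*Upper bound on a changed dose decision.* This supposes that the shorter list is used for the count every time, against the cross-references. The shorter list then sees a DLT rate p = b, and Section 5.1 sees p = b + q.
- Six-patient rule (GFR 30–59 levels, or any level assessed as the HTLD): P(pass) = (1 − p)^6 + 6p(1 − p)^5.
- Escalation rule for GFR ≥ 60, which escalates "if none of the first 3 evaluable patients experience DLT in the first 28 day cycle", or if 1 of 3 is followed by 0 of 3: P(pass) = (1 − p)^3 + 3p(1 − p)^5.

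For example, with b = 0.10 and q = 0.05, the six-patient rule passes with probability 0.886 at p = 0.10 and 0.776 at p = 0.15. The difference is 0.109 before rounding. The escalation rule gives 0.906 and 0.814, a difference of 0.092.

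Probability that a level passes only because of the omission:

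| b | Rule | q = 0.02 | q = 0.05 | q = 0.10 |
|---|---|---|---|---|
| 0.10 | six-patient | 0.041 | 0.109 | 0.230 |
| 0.15 | six-patient | 0.048 | 0.121 | 0.243 |
| 0.20 | six-patient | 0.049 | 0.121 | 0.235 |
| 0.10 | GFR ≥ 60 | 0.035 | 0.092 | 0.198 |
| 0.15 | GFR ≥ 60 | 0.041 | 0.105 | 0.214 |
| 0.20 | GFR ≥ 60 | 0.044 | 0.109 | 0.214 |

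If the shorter list were used in one decision in ten, each entry is multiplied by 0.1. Across both rules this gives about 0.3–0.5%, 0.9–1.2% and 2.0–2.4% for the three values of q.

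**The case against.** The strongest reply is that nothing that matters depends on the shorter lists. Section 5.1 governs the endpoint, the escalation, the accrual stop and the HTLD. Several safeguards would also bring the event to notice. Section 6.2 requires all grade 3 and 4 events to be recorded. Section 10.2.1 has DLT assessed weekly in cycle 1, Section 5.6.1 requires the principal investigator to approve each escalation, and Section 9.2 provides committee review twice a month. The serious adverse event route is faster than the DLT notice. Section 6.1 gives blood dyscrasias without hospitalisation as an example of an important medical event, and Section 6.3.1 requires notice to the company within 24 hours, with participating sites copying the principal investigator. All the rates above are assumed. The one cohort described in detail, six patients at 40 mg/m² twice weekly, had a single DLT, and it was neutropenic fever.

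Most of this stands, and it limits the harm. The dose effect is zero if Section 5.1 is followed, and the pass probabilities are only an upper bound. The 11–47% figures give the chance that such a patient occurs, not that a notice fails. What remains is that the safeguards record or review events without saying which definition classifies this patient. Serious event reporting depends on medical judgment and does not label the event a DLT. The early DLT data are few, and the documents do not say when the transfusion rule was added.

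**Conclusion.** The concern holds. Sections 6.2.1 and 10.2.1 are wrong as written: followed literally, they classify a foreseeable cycle 1 patient differently from Section 5.1. The realistic consequence is a late or missed DLT notice and a DLT table that may not match the dose decision. The decision itself is safe as long as Section 5.1 is applied.

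The size cannot be fixed from the documents. On assumed event rates of 2% to 10%, the chance that a case arises among six patients is 11% to 47%. The chance that a level passes only because of the omission is at most about 3% to 24%. That bound assumes other DLTs in 10% to 20% of patients and the shorter list used for every count. This should be fixed, at the low end of that grade.

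**What to change.** Replace the lists in Sections 6.2.1 and 10.2.1 with a reference to the DLT definition in Section 5.1, or copy the transfusion sentence into both. The reference is better, because it leaves one list to maintain. State that cycle 1 DLT counts for the HTLD and HTLD-CKD (the HTLD for GFR 30–59 ml/min) are tabulated under Section 5.1.

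Check cycle 1 platelet transfusion records for patients treated while the rule was in force, and reclassify any patient who meets it.

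The cost is a wording change and a short record check, with no extra patients. The data should exist: grade 3 and 4 events are recorded with duration and action taken (Section 6.2), and Table 5 asks for blood counts at least twice a week when platelets are transfused. The one drawback is that a dose level may look slightly less tolerable.

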10.2.2 Safety

Data from all subjects who receive any protocol therapy will be included in the safety analyses. Subjects who entered the study and did not receive any protocol therapy and had this confirmed, will not be evaluated for safety. Adverse events will be recorded during the first 12 cycles, graded according to CTCAE v.4.0 whenever possible, and reported for the time points day 1 of cycle 2, 3, 6, 9, and 12 according to dose level treated. Additionally, worst overall toxicity will be reported at each publication.

10.2.3 Response

The response rate (RR= sCR+CR+VGPR+PR) and clinical benefit response rate (CBRR=sCR+CR+VGPR+MR) will be analyzed for the entire study group, and for the 16-22 patients treated at the HTLD / HTLD-CKD according to whether patients had relapsed or refractory disease at study entry. All response categories require two consecutive assessments but the time a response is first reached will be used to calculate response rates after 6 and 12 cycles. Additionally, best response will be reported. If one or more patients on this trial elect to undergo stem cell transplantation, response before mobilization will be reported.

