
twice a week, together with standard dose lenalidomide and low dose dexamethasone in relapsed or refractory myeloma patients in a phase I/II study with 10 additional patients enrolled at the highest tolerated low azacitidine dose to obtain an initial impression of efficacy and to evaluate whether this dose exerts the expected pharmacodynamic effects in myeloma cells before a larger phase II trial may be conducted. In light of new data supporting use of standard-dose azacitidine in myeloid neoplasia patients with kidney dysfunction(14) and GFR-adjusted lenalidomide for myeloma patients(15), amendment 7 extends the safety and preliminary efficacy evaluations to myeloma patients with GFR 30-59 ml/min (Cockroft-Gault). Lenalidomide will be used at a fixed dose of 10mg daily from day 1-21 every 28 days which yielded equal AUC concentrations in myeloma patients with GFR 30-49m/min as 25mg daily from day 1-21 every 28 days in patients with GFR \geq 80 ml/min in a recent study(15). Only two dose levels of azacitidine will be tested. Dose level "CKD 1" will use azacitidine at 40 mg/m² s.c. twice a week which has been found tolerable in patients with GFR \geq 60 ml/min; one of six patients developed a dose limiting toxicity, culture negative neutropenic fever at an absolute neutrophil count (ANC) nadir of 0.48K/mm³, with resolution the next day at an ANC of 0.89K/mm³ without G-CSF use. At the time of amendment 7, two patients with normal kidney function have completed the first cycle at dose level 5 (azacitidine 50mg/m² s.c. twice a week) without dose limiting toxicities. Six patients with GFR 30-59 ml/min will be treated at CKD 1 if dose limiting toxicities (DLTs) do not occur in more than one patient. If 2 of 3 or 2 of up to six patients develop DLTs at CKD1, subsequent patients will be treated at "CKD -1" (30mg/m² s.c. twice a week). Otherwise (no more than one patient with DLTs at CKD1), subsequent patients will receive azacitidine at 50mg/m² s.c. twice a week (= dose level CKD2). Lower or higher dose levels will not be tested. This modified dose escalation scheme increases safety by enrolling at least 6 patients per dose level and guarantees that the tolerability of twice a week azacitidine in patients with GFR 30-59 ml/min will be defined by enrolling maximally 12 additional patients. Omission of weekly azacitidine is based on the observation that clinical benefit response rates were more than twice as high with twice a week than with weekly azacitidine dosing (40% versus less than 15%) in patients with GFR > 60ml/min, an encouraging result taking into consideration that patients had received a median of 4.5 prior regimens, with myeloma refractory to previous lenalidomide in 88%, to previous proteasome inhibitors in 81%, and to both lenalidomide and proteasome inhibitors in 75%. Once the highest tolerated low dose for patients with reduced GFR (HTLD-CKD) has been defined, enrollment at this dose level may contribute to the 10 patient phase II extension. Before amendment 7 eighteen patients have started treatment, including two at dose level 5. Assuming up to 6 patients will be enrolled per dose level; the maximal number of enrolled patients will therefore increase from previously estimated 40 to 44 after amendment 7.

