
STUDY OBJECTIVES:

Primary:

- Define the highest tolerated low doses (HTLD and HTLD-CKD for GFR > 60 ml/min and 30-59ml/min, respectively) and safety of azacitidine given at low but increasing doses up to 50mg/m² twice a week concurrently with GFR-adjusted lenalidomide doses and low dose dexamethasone in patients with relapsed or refractory multiple myeloma.

Secondary:

- Response according to international response criteria (\geq PR) and clinical benefit response (\geq minor response according to adapted EBMT criteria), see under 7
- Correlate response with plasma activity of the azacitidine inactivating enzyme cytidine deaminase (CDA)
- Progression-free survival and overall survival
- Peripheral blood hematopoietic progenitor (CD34+) yield and time to neutrophil and platelet recovery in patients undergoing autologous stem cell transplantation
- Promoter demethylation and gene reactivation in myeloma cells and hematopoietic progenitors treated at the HTLD / HTLD-CKD level after one cycle of therapy
- Changes in global gene expression in myeloma cells treated at the HTLD / HTLD-CKD level after one cycle of therapy

STUDY DESIGN:

Two institutions phase I/II study, classical 3x3 design for patients with GFR \geq 60ml/min, modified 3x3 design for patients with GFR 30-59ml/min, with 10 additional patients treated at the highest tolerated low dose (HTLD / HTLD-CKD).

Patient population: Multiple myeloma, with relapsed or refractory disease (see under 5.3).

The Cockcroft-Gault formula will be used for all GFR estimations throughout this study (Appendix IV).

STUDY ENDPOINTS**Primary:**

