4.1.2 Secondary Study Objectives

- Response according to international response criteria (\geq PR) and clinical benefit response (\geq minor response according to adapted EBMT criteria), see under 7
- Correlate response with plasma activity of the azacitidine inactivating enzyme cytidine deaminase (CDA)
- Progression-free survival and overall survival
- Peripheral blood hematopoietic progenitor (CD34+) yield and time to neutrophil and platelet recovery in patients undergoing autologous stem cell transplantation
- Promoter demethylation and gene reactivation in myeloma cells and hematopoietic progenitors treated at the HTLD / HTLD-CKD level after cycle 1
- Changes in global gene expression in myeloma cells treated at the HTLD / HTLD-CKD level after cycle 1

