Partial response (PR)	$\geq 50\%$ reduction of serum M protein and reduction in 24-h urinary M protein by $\geq 90\%$ or to <200mg per 24 h, if the serum and urine M protein are unmeasurable, a $\geq 50\%$ decrease in the difference between involved and uninvolved sFLC levels is required in place of the M protein criteria, if the only measurable disease is in the bone marrow, a $\geq 50\%$ reduction in bone marrow plasma cells is required, provided the baseline percentage was $\geq 30\%$. In addition to the above criteria, if present at baseline, a $\geq 50\%$ reduction in the size of soft tissue plasmacytomas is required.
Minor response (MR)	$\geq 25\%$ but $\leq 49\%$ reduction of serum M protein and reduction in 24 h urine M protein by 50–89%, which still exceeds 200mg per 24 h. In addition to the above criteria, if present at baseline, 25–49% reduction in the size of soft tissue plasmacytomas is also required. No increase in size or number of lytic bone lesions (development of compression fracture does not exclude response).

Stable disease (SD)	Not meeting criteria for sCR, CR, VGPR, PR, MR, or progressive disease (see under 5.9.1).
---------------------	---

8 Protocol Amendments/Deviations

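### The clinical benefit response formula in section 10.2.3 leaves out PR, so it falls short of the minor-response-or-better rate in the objectives by the proportion of patients whose best category is PR

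*Combined protocol and SAP*

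**What the plan says.** Two parts of the combined protocol and SAP define the same secondary measure differently.

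- **Objectives.** The secondary objectives in the synopsis and in section 4.1.2 set clinical benefit response at or above "minor response according to adapted EBMT criteria" and refer the reader to section 7.
- **Analysis.** Section 10.2.3 says the "clinical benefit response rate (CBRR=sCR+CR+VGPR+MR) will be analyzed for the entire study group". The same sentence begins "The response rate (RR= sCR+CR+VGPR+PR", so PR is counted in the response rate (RR) but not in the clinical benefit response rate (CBRR).
- **Categories.** Section 7 lists PR and MR as distinct rows. Its stable disease row reads "Not meeting criteria for sCR, CR, VGPR, PR, MR, or progressive disease". MR stops at a 49% fall in serum M protein; PR starts at 50%.
- **Earlier use of the measure.** The synopsis, explaining amendment 7, reports that "clinical benefit response rates were more than twice as high with twice a week than with weekly azacitidine dosing" (40% versus less than 15%). It does not say which categories were counted.

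**The concern.** A clinical benefit rate is meant to be the broader of the two response rates: everyone who responds, plus those with a minor response. The formula in 10.2.3 does not have that property. It drops patients whose best category is PR while keeping those who did less well (MR) and those who did better (VGPR and above).

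An analyst who follows 10.2.3 literally reports a rate that does not answer the stated objective. One who quietly adds PR departs from the written analysis. The 10-patient extension is there to give a first impression of efficacy before any larger phase II trial, and CBRR is one of only two response rates named for it. Clinical benefit rates have also already been used to justify leaving weekly azacitidine out of the cohort with GFR 30-59 ml/min. Later results cannot be set beside those figures until the definition is settled.

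**Working it through.** **Inputs**

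- Written CBRR = (sCR + CR + VGPR + MR)/n, from section 10.2.3.
- RR = (sCR + CR + VGPR + PR)/n, from section 10.2.3.
- Intended CBRR (minor response or better) = (sCR + CR + VGPR + PR + MR)/n, from the synopsis and section 4.1.2 with the categories of section 7.
- n = 16 to 22 at the highest tolerated low dose (HTLD / HTLD-CKD), from section 10.2.3. This agrees with the design: 6 + 10 = 16 for one cohort plus the extension, and 6 + 6 + 10 = 22 for both.
- n up to 44 overall, from section 10.1. This agrees with the synopsis: 18 already started + 4 to complete dose level 5 + 12 with reduced GFR + 10 in the extension = 44.

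The plan states no expected or target CBRR, so there is no figure of its own to reproduce.

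**Can the MR term absorb PR?** No. MR is capped at a 49% serum reduction. If MR were shorthand for MR or better, the sCR, CR and VGPR terms beside it would be redundant.

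**Algebra, each patient counted once by best category**

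1. Intended CBRR − written CBRR = PR/n. One PR patient is worth 1/16 = 6.25 points, 1/22 = 4.5 points or 1/44 = 2.3 points.
2. Written CBRR − RR = (MR − PR)/n, which is negative whenever PR > MR.
3. Intended CBRR = RR + MR/n, so it can never fall below RR.

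**Illustration.** The counts are assumed, because the documents give none: 8 patients at MR or better, of whom 2 are at VGPR or better.

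| n | PR | MR | RR | Written CBRR | Intended CBRR |
|---|---|---|---|---|---|
| 22 | 4 | 2 | 6/22 = 27.3% | 4/22 = 18.2% | 8/22 = 36.4% |
| 22 | 3 | 3 | 5/22 = 22.7% | 5/22 = 22.7% | 8/22 = 36.4% |
| 22 | 2 | 4 | 4/22 = 18.2% | 6/22 = 27.3% | 8/22 = 36.4% |
| 16 | 4 | 2 | 6/16 = 37.5% | 4/16 = 25.0% | 8/16 = 50.0% |
| 16 | 3 | 3 | 5/16 = 31.25% | 5/16 = 31.25% | 8/16 = 50.0% |
| 16 | 2 | 4 | 4/16 = 25.0% | 6/16 = 37.5% | 8/16 = 50.0% |

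**Direction of change.** Section 10.2.3 reports rates after 6 and after 12 cycles. Suppose one patient of 22 deepens from MR to PR between the two, moving the counts from (3 PR, 3 MR) to (4 PR, 2 MR). RR rises from 22.7% to 27.3%, the intended CBRR stays at 36.4%, and the written CBRR falls from 22.7% to 18.2%. A better outcome lowers the reported clinical benefit.

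**The case against.** The strongest reply is that this is a drafting slip that would mislead nobody. RR in the same sentence includes PR, the list skips one rung of an ordered scale, and two statements of the objectives give the intended meaning. Section 10.2.3 also promises best response; if that is tabulated by category, any reader can rebuild the correct rate. CBRR carries no test, threshold or decision rule.

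Most of this is fair. It probably is a slip, and a table of best response would limit the harm. But 10.2.3 is the operative analysis text, nothing in section 10 corrects it, and a conflict between objective and analysis is not settled by guessing which one was meant.

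Two narrower points also deserve an answer.

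- **Counting rule.** The shortfall equals the PR proportion only if each patient is counted once, by best category. Section 10.2.3 uses the time a response is first reached and does not say how a patient who passes from MR to PR is handled. If a confirmed MR on the way counted towards the MR term, the shortfall would be smaller. The additive form of RR makes one category per patient the natural reading, but it remains a condition.
- **Denominators.** The HTLD / HTLD-CKD results are to be given by relapsed or refractory status, so the reported denominators may be smaller than 16 to 22. Each PR patient would then weigh more, not less.

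The synopsis figures of 40% and less than 15% are background, not an endpoint. Their unstated definition is a query, not further evidence of error.

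**Conclusion.** The concern holds. As written, CBRR is not the measure named in the objectives, and no reading of the documents repairs the formula. It is too low by PR/n and can fall below RR.

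This rests on one best category per patient. The size in this trial is unknown because no PR or MR counts are given; it is zero if no patient has PR as best category. The percentages in the table illustrate assumed counts and are not predictions.

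The effect is confined to one descriptive secondary rate. RR is correctly specified, and the primary endpoint, dose escalation and sample size are untouched. It should be fixed because following the text literally gives a wrong result and the correction is trivial.

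**What to change.** In section 10.2.3, change the formula to CBRR = sCR + CR + VGPR + PR + MR, in line with the synopsis and section 4.1.2.

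Optionally, add one sentence to the synopsis saying whether the quoted clinical benefit rates (40% versus less than 15%) used that definition, so that later results can be compared with them.

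The cost is one added term and, if wanted, one sentence. No new data are needed, and the response categories, visits and treatment rules stay as they are.
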